7.4.2 Modifications of Study Therapy

There will be no dose escalations or reductions of nivolumab allowed. Brentuximab Vedotin may reduce dose to 1.2mg/kg. Brentuximab. Dose reduction as reported by the investigator will be summarized along with reason for reduction.

7.4.2.1 Dose Delays

Treatment may be delayed for up to a maximum of 6 weeks from the last dose. If one of the study drug is delayed for any reason the other drug must also be delayed. A dose will be considered as actually delayed if the delay is exceeding 3 days as of cycle 2 onwards (i.e., greater than or equal to 4 days from scheduled dosing date). Length of delay is defined as (duration of previous cycle in days - 21). Dose delays will be divided into following categories: 4 - < 8 days, 8 - < 15 days, 15 - < 42, ≥ 42 days. Reason for dose delay will be retrieved from CRF dosing pages.

The following parameters will be summarized by drug:

• Number of subjects with at least one dose delayed, number of dose delayed per subject, Length of Delay and Reason for Dose Delay

7.4.2.2 Infusion Interruptions and Rate Changes:

Each nivolumab or brentuximab vedotin infusion can be interrupted and/or the IV infusion rate can be reduced. This information will be retrieved from CRF. The following parameters will be summarized for each drug:

- Number of subject with at least one dose infusion interrupted, number of infusions interrupted per subject and reason for the interruptions.
- Number of subject with at least one IV infusion rate reduction, number of IV infusion rate reduction per subject and reason for the interruptions.

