First dose of nivolumab will be administered on Cycle 1 Day 8, which is only 2 weeks away from Cycle 2 Day 1. For safety reasons, subjects may be dosed no less than 12 days between doses. For all other cycles, treatment is to occur within 3 days of the scheduled dosing date. Dose given after the 3 day window is considered a dose delay. Treatment may be delayed for up to a maximum of 6 weeks from the previous dose. Refer to [Section 4.5.4](#) for further details.

Subjects will be monitored continuously for AEs while on study. Treatment modifications (eg, dose delay, interruption or discontinuation) will be based on specific laboratory and AE criteria (further details described in [Section 4.5.3](#) and [Section 4.5.4](#)).

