4.5.4 Dose Modifications for Nivolumab

4.5.4.1 Nivolumab Dose Delays

Dose delay criteria apply for all drug-related AEs. Nivolumab must be delayed until treatment can resume (see [Section 4.5.4.2](#))

Nivolumab administration should be delayed for the following:

- Any Grade ≥ 2 non-skin, drug-related AE, with the following exceptions:
 - Grade 2 drug-related fatigue or laboratory abnormalities do not require a treatment delay
- Any Grade 3 skin, drug-related AE

- Any Grade 3 drug-related laboratory abnormality, with the following exceptions for lymphopenia, leukopenia, AST, ALT, total bilirubin, or asymptomatic amylase or lipase:
 - Grade 3 lymphopenia or leukopenia does not require dose delay.
 - If a subject has a baseline AST, ALT, or total bilirubin that is within normal limits, delay dosing for drug-related Grade ≥ 2 toxicity.
 - If a subject has baseline AST, ALT, or total bilirubin within the Grade 1 toxicity range, delay dosing for drug-related Grade ≥ 3 toxicity.
- Any AE, laboratory abnormality, or intercurrent illness which, in the judgment of the investigator, warrants delaying the dose of study medication.

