8.3 Endpoints

8.3.1 Primary Endpoint(s)

The primary safety endpoints include incidence of deaths, adverse events, serious adverse events, adverse events leading to discontinuation, adverse events leading to dose delay, drug-related adverse events and specific laboratory abnormalities (worst grade). Toxicities will be graded using the National Cancer Institute (NCI) Common Terminology Criteria for Adverse Events (CTCAE) version 4.03.

The primary efficacy endpoint is ORR. It is defined as the number of subjects with a best overall response (BOR) of confirmed CR or PR divided by the number of treated subjects. The BOR is defined as the best response designation recorded between the date of first dose and the date of initial objectively documented progression or the date of subsequent therapy, whichever occurs first. Allogeneic SCT and ASCT will be considered as subsequent therapy. In subjects with relapsed refractory DLBCL, relapsed refractory PTCL, relapsed refractory PMBL and relapsed refractory MGZL the response (CR, PR, PD, and progression) will be assessed according to Lugano Classification 2014. For subjects with relapsed refractory CTCL, response will be assessed according to consensus Global Response Score as per the consensus statement of the International Society for Cutaneous Lymphoma. A CR must have been confirmed by scans, including a negative Positron Emission Tomography (PET) to be considered for CR in subjects with PTCL, DLBCL, PMBL and MZGL. In subjects with PTCL, if the bone marrow was compromised at baseline, a bone marrow must also be negative at the time of CR. In CTCL CT scans (chest, neck, abdomen and pelvis), blood flow for SS cells and m SWAT skin scoring along with medical photography will be performed at baseline and at the end of the treatment for response evaluation. The investigator will perform tests that will allow evaluation of response to therapy according to corresponding disease criteria in [Appendix 2](#) and [Appendix 4](#). The analysis of the primary endpoint will occur approximately 8 months after the last enrolled subject's first dose of study therapy. Depending on the enrollment for each disease cohort, the analysis may be done at different times for each cohort, or at the same time for the three cohorts.

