7.4.1 Administration of Study Therapy

The following parameters will be summarized (descriptive statistics) for each drug separately:

- Number of doses received
- Cumulative dose
- relative dose intensity
- Duration of treatment: duration of treatment will be presented using a Kaplan-Meier curve whereby the last dose date will be the event date for subjects who discontinued study therapy. Subjects who are still on study therapy will be censored on their last dose date. Median duration of treatment and associated 95% CI will be provided.

A by-subject listing of dosing of study medication (record of study medication, infusion details, dose change) and a listing of batch number will be also provided.

Below table summarizes the key parameters used to calculate dosing data.

	Nivolumab	Brentuximub Vedotin
Dosing schedule per protocol	Day 1, 240mg every 3 weeks (except cycle 1 C1D8)	1.8mg/kg (or 1.2mg/kg) every 3 weeks
Dose	Dose is defined as total dose administered. Dose administered in mg at each dosing date are collected on the CRF.	Dose (mg/kg) is defined as total dose administered (mg)/most recent weight. Dose administered in mg at each dosing date and most recent weight are collected on the CRF.
Cumulative Dose	Cum dose (mg) is sum of the doses (mg) administered to a subject during the treatment period.	Cum dose (mg/kg) is sum of the doses (mg/kg) administered to a subject during the treatment period.
Duration of treatment	Last dose date - Start dose date + 1	Last dose date - Start dose date + 1
Relative Dose intensity	If only one dose of nivolumab Cum dose (mg)/[(Last dose date of nivolumab - Start dose date of nivolumab + 14) x 240 /14] x 100	Cum dose (mg/kg)/[(Last dose date of BV - Start dose date of BV + 21) x 1.8 /21] x 100 or

Nivolumab	Brentuximub Vedotin
If more than 1 dose of nivolumab	
[Cum dose (mg) / (Last dose date of nivolumab - Start dose date of nivolumab + 21)] x [(14+(number of nivolumab doses-1) * 21 / 240 * number of nivolumab doses] x 100	

Table 7.4.1 -1: Administration of Study Therapy: Definition of Parameters

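### SAP 7.4.2.1 counts dose delays only from cycle 2, so a late first nivolumab dose (due Cycle 1 Day 8) is never classed as a nivolumab delay, and nivolumab dose intensity can read above 100% when that dose is late

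*SAP*

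**What the plan says.** SAP 7.4.2.1 sets the counting rule: "A dose will be considered as actually delayed if the delay is exceeding 3 days as of cycle 2 onwards". It then sets the measure: "Length of delay is defined as (duration of previous cycle in days - 21"). It adds that "The following parameters will be summarized by drug": subjects with at least one delayed dose, delayed doses per subject, length of delay and reason.

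The nivolumab schedule in SAP Table 7.4.1-1 is "Day 1, 240mg every 3 weeks (except cycle 1 C1D8"). Protocol 4.5 explains the first interval: "First dose of nivolumab will be administered on Cycle 1 Day 8, which is only 2 weeks away from Cycle 2 Day 1". It sets a 12-day minimum between doses, and it states the 3-day dosing window and the definition of a delay for the other cycles.

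Protocol 4.5.4.1 says "Dose delay criteria apply for all drug-related AEs", with no exception for cycle 1. Protocol 4.5.4.2 says that when nivolumab is delayed, brentuximab vedotin is delayed as well and the combination resumes on Day 1 of the next cycle.

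For more than one nivolumab dose, the actual-dose part of relative dose intensity in Table 7.4.1-1 is "Cum dose (mg) / (Last dose date of nivolumab - Start dose date of nivolumab + 21"), so the clock starts at the actual first nivolumab dose.

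**The concern.** The first nivolumab dose is the only dose in the regimen that is not due on Day 1 of a cycle, and it is given after a week of brentuximab vedotin alone. Protocol Table 5.1-2 schedules laboratory tests and vital signs before it, so a toxicity-driven hold at that visit is foreseeable. The SAP rule excludes this dose in two ways: it lies before cycle 2, and it has no previous cycle whose duration could be measured. The dose-limiting-toxicity definition (Protocol 4.5.1, SAP 7.6.1) does not fill the gap, because its delay component refers to cycle 2 and to Cycle 3 Day 1.

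Safety and tolerability of the combination are a primary objective. A by-drug delay table that cannot register a late first nivolumab dose, beside a dose-intensity figure that can rise because of it, would describe that first week incorrectly.

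**Working it through.** **Inputs.** Planned nivolumab days are 8, 22, 43 and so on (SAP Table 7.4.1-1). The planned first gap is 14 days and the minimum gap 12 days (Protocol 4.5). A delay counts if it is 4 days or more, from cycle 2 (SAP 7.4.2.1). The documents state no delay count or dose-intensity value to reproduce.

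**Delay rule.** Let the first dose be *d* days late, on day 8 + *d*, and let *g* be the gap to the second dose on Cycle 2 Day 1. Cycle 2 Day 1 then falls on day 8 + *d* + *g*, but not before day 22. The SAP length of delay is that day minus 22.

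| Path after a late Day 8 dose | SAP length of delay | Counted? |
|---|---|---|
| *g* = 12, *d* = 4 | 24 − 22 = 2 | No |
| *g* = 12, *d* = 5 | 25 − 22 = 3 | No |
| *g* = 12, *d* = 6 | 26 − 22 = 4 | Yes, against cycle 2 |
| *g* = 14, *d* ≥ 4 | *d* | Yes, in full, against cycle 2 |
| First dose moved to an on-time Cycle 2 Day 1 (14 days late) | 22 − 22 = 0 | No |

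These figures count cycle 1 from brentuximab vedotin Day 1. The SAP does not say so. Counted from the first nivolumab dose, an on-time second dose would give 14 − 21 = −7 days.

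**Dose intensity.** The printed formula has an unbalanced bracket. Read as [cumulative dose / (last − first + 21)] × [(14 + 21(*n* − 1)) / (240*n*)] × 100, it gives exactly 100% on schedule for *n* = 2, 3, 4, 8 and 16. Read literally by operator precedence, it gives 19,440% for two on-schedule doses. With full 240 mg doses the first reading reduces to

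(14 + 21(*n* − 1)) / (last − first + 21).

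If doses after the second stay 21 days apart:

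| First gap | *n* = 2 | *n* = 4 | *n* = 8 |
|---|---|---|---|
| 12 days | 35/33 = 106.1% | 77/75 = 102.7% | 161/159 = 101.3% |
| 13 days | 35/34 = 102.9% | 77/76 = 101.3% | 161/160 = 100.6% |
| 14 days | 100% | 100% | 100% |
| 21 days (first dose on Cycle 2 Day 1) | 35/42 = 83.3% | 77/84 = 91.7% | 161/168 = 95.8% |

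The separate one-dose formula gives 100% for a single full dose, whatever day it is given.

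**Clock started at planned Day 8.** The first date in the denominator becomes day 8.
- *d* = 2, Cycle 2 Day 1 on time: 100% for each *n*.
- *d* = 5, Cycle 2 Day 1 three days late: 35/38 = 92.1%, 77/80 = 96.2% and 161/164 = 98.2%, in place of 106.1%, 102.7% and 101.3%.

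**The case against.** The strongest reply is that the SAP follows the protocol. Protocol 4.5 gives Cycle 1 Day 8 only a minimum interval to the next dose and states its window for the other cycles. This stands: a reader might infer that the SAP departs from the protocol, and it does not. A threshold for Day 8 lateness is therefore an analysis convention. It does not make the by-drug table informative about the first nivolumab dose.

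A reader might also infer that dose intensity will look systematically too good. The documents do not support that. The excess needs a gap of 12 or 13 days. It is nil at 14 days, and the figure falls if the held dose moves to Cycle 2 Day 1, which is one reading of Protocol 4.5.4.2. Likewise, with a 14-day gap a hold of 4 days or more is counted at full length, although against cycle 2.

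A third inference is that the primary safety endpoint "adverse events leading to dose delay" (Protocol 8.3.1) is understated. SAP 7.6.5 defers that analysis to the Core Safety SAP, which is not among the documents, so nothing shows that the rule in 7.4.2.1 governs it.

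Finally, SAP 7.4.1 provides a by-subject dosing listing, so late first doses stay traceable. That softens the problem but does not correct the summary tables.

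**Conclusion.** The gap is real and limited. Under SAP 7.4.2.1 a late Cycle 1 Day 8 nivolumab dose is never a nivolumab delay in its own right. Depending on what follows, it leaves no trace in the delay table (4 or 5 days late with a 12-day gap, or 14 days late with an on-time Cycle 2 Day 1) or appears only as a cycle 2 delay. Within the 12-day minimum, dose intensity can be overstated to at most 106.1% at two doses, shrinking to 101.3% at eight.

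This rests on the bracket reading that returns 100% on schedule, full 240 mg doses, 21-day intervals after the second dose, and cycle 1 counted from brentuximab vedotin Day 1. The effect is on descriptive exposure and tolerability summaries; ORR and its confidence interval are untouched. The documents give no rate of late Day 8 doses, so the number of subjects affected cannot be stated. The point is worth correcting because a stated rule gives a misleading summary for a primary objective and the repair is small.

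**What to change.** These are analysis conventions only; no dosing rule is proposed.

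- **Separate row.** In SAP 7.4.2.1 add a nivolumab row for Cycle 1 Day 8 timing. Lateness = (first nivolumab date − Cycle 1 Day 1 date) − 7, reported with reason and using the existing category of more than 3 days.
- **Anchor.** State that cycle duration is counted from brentuximab vedotin Day 1 of the previous cycle for both drugs.
- **No double counting.** Keep the Day 8 row apart from the count from cycle 2 onward, or flag the two as one episode. Otherwise a 10-day hold followed by a 12-day gap would appear as a 10-day delay and again as an 8-day delay at cycle 2.
- **Dose intensity.** In Table 7.4.1-1 start the nivolumab clock at planned Day 8 (Cycle 1 Day 1 + 7), in the one-dose line as well, and correct the unbalanced bracket.

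The cost is SAP wording and minor programming, using dosing dates already collected on the CRF. Delay and dose-intensity figures may look less favourable, in most cases slightly. The change is larger when the first dose moves to Cycle 2 Day 1: at two doses, 35/(43 − 8 + 21) = 35/56 = 62.5% instead of 83.3%.

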7.4.2.3 Discontinuation of Study Therapy

The number and percentage of subjects who have discontinued all study drugs and reason for discontinuation will be summarized by treatment group and overall using the subject status eCRF page from end of treatment.

In addition, subjects who discontinued one drug, while continuing treatment with the other study drug, will be summarized based on the dose modification CRF. The reason for discontinuing a specific drug from the combination will also be summarized.

7.5 Efficacy Analyses

7.5.1 Primary Efficacy Endpoint

The primary endpoint ORR will be summarized for all treated subjects by binomial response rate and its corresponding two-sided 80% exact CIs using the Clopper-Pearson method.

BOR categories will be tabulated.

7.5.2 Secondary Efficacy Endpoints

The CR will be analyzed using the same statistical method as ORR.

The DOR will be summarized for subjects who achieve PR or CR using the Kaplan-Meier (KM) product-limit method. Median values of DOR, along with two-sided 95% CI using log-log transformation method. Range of DOR will also be calculated. The same analysis will be performed for duration of CR.

The time to response (TTR), time from the first dose to the first response date will also be summarized. Note that TTR was not listed as a secondary endpoint in the protocol.

PFS will be summarized descriptively using the Kaplan-Meier (KM) product-limit method. KM curve of PFS will be generated. Median values of PFS, along with two-sided 95% CIs (based on the log-log transformation), will be calculated. PFS rates at 6 and 12 months (and two-sided 95% CIs) may be reported in function of the the minimum follow-up at time of analyses. Subject listings of PFS will be produced.

The source of progression (death vs. progression) will be summarized. The status of subjects who are censored in the PFS Kaplan-Meier analysis will be tabulated using following categories:

- Received subsequent anti-cancer therapy
- Still on-treatment

- Progression-free in follow-up
- Off-study: (lost to follow-up, withdrew consent, other).

OS will be analyzed using the same statistical method as PFS. Median values of OS, survival rates at 6 and 12 months along with two-sided 95% CIs may be reported in function of the minimum follow-up at time of analyses.

The status of subjects who are censored in the OS Kaplan-Meier analysis will be tabulated using the following categories:

- On-study (on-treatment and not progressed, on-treatment progressed, in follow-up);
- Off-study: (lost to follow-up, withdrew consent, etc.).

Subject Follow-up

The extent of follow-up for survival defined as the time between first dose date and last known date alive (for subjects who are alive) or death date (for subjects who died) will be summarized descriptively (mean, standard deviation, median, first and third quartiles, minimum, maximum) for all treated subjects.

Follow-Up Therapy

The following information pertaining to subsequent therapies will be summarized:

- Systemic therapy by drug name
- Hematopoietic stem cell transplantation (Allogeneic, Autologous)
- Surgery
- Radiotherapy

A subject listing of follow-up therapy will be produced for subjects who had any subsequent therapy.

7.6 Safety Analyses

Safety analyses will be performed in all treated subjects. Descriptive statistics of safety will be presented using National Cancer Institute (NCI) Common Terminology Criteria for Adverse Events (CTCAE) version 4.03. All on-study AEs, drug-related, AEs, SAEs and drug-related SAEs will be tabulated using worst grade per NCI CTCAE v4.03 criteria by system organ class and MedDRA preferred term. On-study lab parameters including hematology, chemistry, liver function, thyroid function, and renal function will be summarized using worst grade per NCI CTCAE v4.03 criteria. Details are in the Core Safety SAP v3.0.

7.6.1 Dose Limiting Toxicities

The DLT evaluation period, which consists of the first dose of study drug through the first 6 weeks of treatment, will be conducted in the first 6 treated subjects.

DLTs are defined as any study drug-related toxicity (brentuximab vedotin or nivolumab) that requires either a dose reduction or delay of more than 7 days of either study drug in Cycle 2 or delays the Cycle 3 Day 1 administration of combined treatment by more than 7 days.

Cohort A subjects who have a related AE that require either discontinuation, dose reduction or delay of more than 7 days of either study drug in Cycle 2 or delays the Cycle 3 Day 1 will be categorized as experiencing DLT.

- Number of subjects with dose limiting toxicities will be tabulated (cohort A, all treated subjects)
- A listing will be provided of those subjects containing their reasons for drug discontinuations, delay or reduction and total number of courses received (Cohort A, All treated subjects)

7.6.2 Deaths

See Core Safety SAP

7.6.3 Serious Adverse Events

See Core Safety SAP

7.6.4 Adverse Events Leading to Discontinuation of Study Therapy

See Core Safety SAP

7.6.5 Adverse Events Leading to Dose Delay of Study Therapy

See Core Safety SAP

7.6.6 Adverse Events

See Core Safety SAP

7.6.7 Adverse Events by Subgroups

See Core Safety SAP

7.6.8 Multiple Events

See Core Safety SAP

7.6.9 Adverse Events of Special Interest

See Core Safety SAP

7.6.9.1 Transplant

Number and percentage of subjects by response category (CR, non-CR, unable to determine) will be provided at the time of transplant and at the 100 days, 6 months and 1 year timepoints after transplant for subjects undergoing subsequent allogeneic SCT and autologous SCT separately. Denominators will be based on subjects with assessment available by timepoint.

For subjects undergoing allogeneic SCT, number and percentage of subjects with GVHD will be provided at the 100 days, 6 months and 1 year timepoints: chronic limited, chronic extensive, acute (grade I, II, III, IV, unknown). Denominators will be based on subjects undergoing allogeneic SCT with assessment available by timepoint.

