3.6 Post Study Drug Study Follow up

In this study, overall survival is a key endpoint of the study. Post study follow-up is of critical importance and is essential to preserving subject safety and the integrity of the study. Subjects who discontinue study drug must continue to be followed for collection of outcome and/or survival follow-up data as required and in line with [Table 5.1-3](#) until death, withdrawal of consent, lost to follow-up or the conclusion of the study.

In addition, subjects who discontinue study therapy by proceeding to allogeneic SCT or ASCT will require tumor assessment (CR or non-CR) by the investigators according to the Lugano Classification 2014 (DLBCL/PTCL) and consensus Global Response Score (CTCL) on day 100, at 6 months, 1 year and every year thereafter from the date of stem cell infusion until the first non-CR after SCT is documented. For the subjects who discontinue study therapy by proceeding to allogeneic SCT, documentation of acute and chronic GVHD will be simultaneously collected see [Appendix 5](#) for more details.

Subjects who discontinue study drug may continue to be followed. BMS may request that survival data be collected on all *treated* subjects outside of the 3 month specified visit schedule. At the time of this request, each subject will be contacted to determine their survival status unless the subject has withdrawn consent for all contact.

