4.5.9.3 Discontinuation due to “Further Progression”

Subjects should discontinue study therapy upon evidence of further progression, defined as an additional 10% or greater increase in tumor burden volume from time of initial progression (including all target lesions and new measurable lesions, increase in tumor burden without a 5mm absolute increase does not require discontinuation) from previous PET-CT, CT and/or MRI.

- The tumor burden volume from time of initial progression should be used as the reference baseline for comparison with the post-progression assessment.
- New lesions are considered measurable at the time of initial progression if the long axis is more than 15 mm regardless of the short axis. Increase in tumor burden without a 5mm absolute increase does not require discontinuation.
- Any new lesion considered non-measurable at the time of or after initial progression may become measurable and therefore included in the tumor burden determination.

4.5.9.4 Efficacy Assessment for Subjects who Discontinue Study Drug during Post-Progression Treatment

When subjects stop post-progression treatment, no additional radiographic assessment will be required and they will continue in the follow-up phase of the study ([Table 5.1-3](#)). The subjects who proceed to allogeneic SCT or ASCT will be followed with specific tumor assessment on day 100, at 6 months, 1 year and every year thereafter from the date of stem cell infusion until the first non-CR after SCT is documented.

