Laboratory Tests	X		Required for X01: CBC with differential, uric acid, serum urea level, serum creatinine, sodium, potassium, calcium, magnesium, chloride, glucose, AST, ALT, total bilirubin, alkaline phosphatase, LDH, TSH (reflex to free T3, free T4 for abnormal TSH result). Panel should also be performed at X02 if X01 results were abnormal.
Pregnancy Test (WOCBP only)	X		Serum or urine

Table 5.1-3: Follow-up Assessments (CA209436)			
Follow-up Assessments (CA209436)			
Procedure	Follow Up, Visits 1 and 2^a (X01 & X02)	Survival Follow-Up Visits^b	Notes
Efficacy Assessments			
Radiographic Tumor Assessment CT chest, CT/MRI abdomen, pelvis, and any other known sites of disease FDG PET-CT (DLBCL, CTCL, PMBL & MGZL only)	X	X	Only for subjects without documented progression since first dose of study therapy Tumor assessments will occur at Week 6 and Week 12 continuing every 9 weeks (+/- 1 week) for the subsequent 4 tumor assessment timepoints, regardless of dosing schedule. After the first year, tumor assessments are to occur every 12 weeks (+/- 2 weeks) until disease progression is documented. FDG PET-CT is required for assessment of DLBCL/PTCL/PMBL/MGZL subjects NOTE: Subjects proceeding to allogeneic SCT or ASCT will be assessed on Day 100, at 6 months, 1 year and every year thereafter from the date of stem cell infusion until the first non-CR after SCT is documented. Refer to section 5.4 for further details.
Blood tumor burden assessment (SS-CTCL only)	See note	See note	Only required to confirm CR in CTCL SS subjects in case blood was positive for tumor cells at screening. Refer to section 5.4.3.6 for details.
Modified Severy Weighted Assessment Tool for subjects with Cutaneous T Cell Lymphoma	See note	See note	Required for subjects with Cutaneous T Cell Lymphoma as part of disease assessment. Refer to Appendix 4 for details.
Medical Photography	See note	See note	Suggested for subjects with Cutaneous T Cell Lymphomas as part of disease assessment. To be done along with the radiographic assessment for all of those respective timepoints. Refer to section 5.4.3.5 for details.

Table 5.1-3: Follow-up Assessments (CA209436)			
Follow-up Assessments (CA209436)			
Procedure	Follow Up, Visits 1 and 2^a (X01 & X02)	Survival Follow-Up Visits^b	Notes

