The primary analysis of the study will be performed 8 months after the last subject has received the first dose of study medication, or earlier if that subject discontinues study therapy. After the cut off for the primary analysis, subjects who are receiving study treatment can continue treatment per protocol until progression, unacceptable toxicity, withdrawal of consent, or other reasons as listed in [Section 3.5](#).

Once subjects discontinue study therapy by proceeding to allogeneic SCT or ASCT, they will not undergo radiographic assessments at the predetermined timepoints described in [Table 5.1-3](#). Instead, they will be evaluated on **Day 100, at 6 months, 1 year and every year thereafter from the date of stem cell infusion** until the first non-CR after SCT is documented.

Sites are required to have available on site all of the on-study tumor scans.

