7 STATISTICAL ANALYSES

7.1 General Methods

All analyses will be performed on the all treated subjects and will be conducted separately for the NHL subtype groups (DLBCL, CTCL, PTCL, PMBL, MGZL).

As there was only one dose explored in the dose evaluation cohort A (brentuximab vedotin 1.8mg/kg and nivolumab 240mg) subjects from cohort A (dose evaluation) and cohort B (dose expansion) will be combined for all analyses, unless otherwise noted. A couple of safety analysis will be conducted on the cohort A subjects only to support the dose evaluation process (see Section 7.6.1).

The bulleted titles in the following subsections describe tabulations of discrete variables, by the frequency and proportion of subjects falling into each category, grouped by cohort. Percentages given in these tables will be rounded and, therefore, may not always sum to 100%. Continuous variables will be summarized by cohort using the mean, standard deviation, median, minimum and maximum values.

Time to event distribution (i.e. progression free survival, overall survival and duration of response) will be estimated using Kaplan Meier techniques.

Median survival time along with 95% CI will be constructed based on a log-log transformed CI for the survivor function $S(t)^{4,5}$. Rates at fixed timepoints will be derived from the Kaplan Meier estimate and corresponding confidence interval will be derived based on Greenwood formula⁶ for variance derivation and on log-log transformation applied on the survivor function $S(t)^7$.

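### Post-transplant CR percentages at 6 months and 1 year omit subjects whose assessment ended at an earlier non-CR, so they overstate CR unless those subjects return to CR at the reported rate or better

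*SAP*

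**What the plan says.** SAP 7.6.9.1 (Transplant) reports the number and percentage of subjects in CR, in non-CR or not determinable. It does so at transplant and at three later timepoints (100 days, 6 months, 1 year), separately for allogeneic and autologous transplant. The denominator rule is "Denominators will be based on subjects with assessment available by timepoint". The same section tabulates GVHD in allogeneic recipients at the three later timepoints, again over those assessed.

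Protocol 3.6 sets the assessment schedule after transplant and ends it with the words "until the first non-CR after SCT is documented". Section 4.5.9.4 repeats the schedule (subjects "will be followed with specific tumor assessment on day 100, at 6 months, 1 year and every year thereafter") with the same ending, as does Table 5.1-3 ("Subjects proceeding to allogeneic SCT or ASCT will be assessed on Day 100, at 6 months, 1 year"). Section 5.4 adds that once subjects go to transplant "they will not undergo radiographic assessments at the predetermined timepoints", so routine scans do not fill the gap. In Table 5.1-3 the GVHD assessments carry the same stop.

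SAP 7.5.2 (Follow-Up Therapy) separately summarises "Hematopoietic stem cell transplantation (Allogeneic, Autologous" transplantation, so the number transplanted by type will be available. The SAP has no rule that carries an earlier post-transplant non-CR forward to later timepoints.

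**The concern.** Each rule is reasonable alone, but together they make availability at 6 months and 1 year depend on the outcome being reported. A subject in non-CR at day 100 has no scheduled later assessment and drops out of both later denominators. A subject first in non-CR at 6 months drops out at 1 year. Subjects who die drop out as well. The later percentages then describe only subjects with no earlier documented post-transplant non-CR, and they can rise while the number in CR falls.

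A reader would naturally take them as CR rates after transplant following the combination. The figure at the time of transplant is unaffected. The day-100 figure, being the first post-transplant visit, is affected only by deaths or missed visits.

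**Working it through.** The plan states no figure to reproduce, so the check is algebra followed by an illustration.

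**General result.** At a visit, let *m* subjects be assessed, of whom *x* are in CR. Let *d* subjects no longer be assessed because of an earlier post-transplant non-CR, with a share *q* of them in CR at that visit. Then:

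- Reported: *p* = *x*/*m*
- Among all transplanted: (*x* + *qd*)/(*m* + *d*)
- Difference: *p* − (*x* + *qd*)/(*m* + *d*) = *d*(*p* − *q*)/(*m* + *d*)

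With *d* > 0, the report is too high exactly when *q* < *p*, correct when *q* = *p*, and too low when *q* > *p*. This treats earlier non-CR as the only reason for not being assessed.

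**Size.** The documents give no transplant numbers or outcomes, so these inputs are assumptions: day-100 CR *c* from 0.5 to 0.9; CR retention *r* from 0.7 to 0.9 in each later interval; *q* as shown; no deaths.

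- Reported at 6 months and at 1 year: *r*
- All transplanted, 6 months: *cr* + (1 − *c*)*q*
- All transplanted, 1 year: *cr*² + (1 − *cr*)*q*

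At *q* = 0 the ratio of reported to all-transplanted is 1/*c* at 6 months: 1/0.9 = 1.11 to 1/0.5 = 2.00. At 1 year it is 1/(*cr*): 1/(0.9 × 0.9) = 1.23 to 1/(0.5 × 0.7) = 2.86. Over the grid:

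| Share back in CR (*q*) | Ratio at 6 months | Ratio at 1 year |
|---|---|---|
| 0 | 1.11-2.00 | 1.23-2.86 |
| 0.2 | 1.08-1.64 | 1.17-1.87 |
| 0.4 | 1.05-1.39 | 1.12-1.44 |
| 0.6 | 1.01-1.20 | 1.06-1.22 |

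Overstatement ends only when *q* reaches *r*, that is, 70-90% here.

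**Example.** Ten subjects are transplanted; 6, 5 and 4 are in CR at day 100, 6 months and 1 year; none returns to CR.

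| Visit | Reported | Of all transplanted |
|---|---|---|
| Day 100 | 6/10 = 60% | 6/10 = 60% |
| 6 months | 5/6 = 83% | 5/10 = 50% |
| 1 year | 4/5 = 80% | 4/10 = 40% |

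**Immature follow-up.** Protocol 5.4 states: "The primary analysis of the study will be performed 8 months after the last subject has received the first dose". Transplant follows first dose, so anyone first dosed less than a year before the cut-off cannot yet have a 1-year post-transplant visit. Using the raw number transplanted as denominator would therefore not give the right rate either.

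**Table size.** SAP 7.1 says analyses "will be conducted separately for the NHL subtype groups (DLBCL, CTCL, PTCL, PMBL, MGZL", and 7.6.9.1 splits by transplant type, giving 5 × 2 groups. Protocol 3.3.1 requires prior ASCT or ASCT ineligibility for DLBCL, PMBL and MGZL, which are (40 + 30 + 10)/130 = 62% of planned expansion subjects. Cells are likely to be small, and one or two dropped subjects can move a percentage a long way.

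**The case against.** The strongest objection is to the reading of the schedule. The stopping clause could be taken to limit only the open-ended yearly visits, leaving day 100, 6 months and 1 year fixed for everyone. The stopping-rule bias would then vanish, and only deaths, missed visits and immature follow-up would remain. That reading is possible. However, in each place the clause closes one continuous visit list, and applying it to the whole list is the more natural reading. Deaths would leave the denominator under either reading.

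Second, the denominator rule is disclosed and counts are shown. In the ten-subject example a careful reader could recover 5/10 and 4/10. That is true for that simple case. It fails once some subjects have died, missed a visit or not reached the timepoint, because the table does not separate these from earlier non-CR.

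Third, the exact threshold depends on earlier non-CR being the only cause of absence. Deaths counted as not in CR add to the overstatement; missed or unreached visits can move it either way. The SAP does not say whether an undeterminable response counts as an available assessment. If it does, it stays in the denominator and lowers the reported percentage. These limits stand, but they do not remove the bias.

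Fourth, the table is descriptive, sits in the safety section and supports no objective. The fold-changes are illustrative, with the largest at the no-return corner. Also, prior ASCT or ASCT ineligibility does not preclude a later allogeneic transplant, so the 62% is only a rough guide to table size. All of this is accepted and limits the importance of the point.

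**Conclusion.** The point holds. Following both documents as written, the 6-month and 1-year CR percentages are conditional on no earlier documented post-transplant non-CR. They overstate CR among all transplanted subjects unless the returning share is at least the reported percentage. This rests on the stop applying to every post-transplant visit, on at least one earlier non-CR occurring, and, for the exact threshold, on no other reason for absence.

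Under the assumed ranges the overstatement runs from about 1% (60% returning, 6 months) to 2.9-fold (none returning, 1 year). The actual size in this trial cannot be known from the documents. GVHD counts after non-CR are incomplete for the same reason, with no known direction of error. Importance is low to moderate: the table should be corrected, but no efficacy endpoint depends on it.

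**What to change.** In SAP 7.6.9.1, for the CR table at 100 days, 6 months and 1 year:

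- **Denominator:** all subjects who received that transplant type and whose potential follow-up, from infusion date to data cut-off, reaches the timepoint.
- **Numerator:** subjects in CR at the visit with no earlier documented non-CR after transplant and no death, labelled as maintained CR. Response at the time of transplant does not count as an earlier non-CR, so a subject transplanted in non-CR and in CR at day 100 counts as CR.
- **Separate rows:** earlier post-transplant non-CR, death, unable to determine, and missing.

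For GVHD, add the number of allogeneic recipients no longer assessed because of earlier non-CR or death. Add a footnote that scheduled ascertainment ends at the first non-CR after transplant.

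The cost is SAP wording and slightly more table programming, using data already collected; no assessment schedule changes. The CR percentages will look less favourable, and maintained CR understates CR if subjects convert later without being observed. The GVHD note makes the missing ascertainment visible but does not recover it. A footnote calling the present percentages conditional would prevent the misreading, but it would not supply a rate for the transplanted group.
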